Theoretical underpinnings of Resourcefulness Training posit that caregivers with greater resourcefulness will experience less stress and, as a result, will augment their caregiving capacity. This intervention involves the following components: 1) a face-to-face session for teaching social (help-seeking) and personal (self-help) resourcefulness skills **using a 32 minute video**, 2) ongoing access to video vignettes of parents of technology-dependent children describing the application of resourcefulness skills in daily life, 3) 4 weeks of skills' reinforcement using daily journal writing by the parents, and 4) weekly phone calls from the intervention nurse over 4 weeks after face-to-face intervention training. Booster sessions for the intervention group at 2 and 4 months post-intervention consist of a phone call and one week of journal writing. The Attention Control group will receive weekly phone calls for the first four weeks plus any usual care. In this exploratory stage of intervention work, we will evaluate the impact of the intervention on psychological and physical outcomes and family outcomes (family functioning) over time and whether changes in resourcefulness skills mediate these outcomes.

The specific aims of the study are to: Aim 1: Determine whether Resourcefulness Training versus Attention Control improves psychological (general mental health, depressive cognitions, depressive symptoms, appraised stress, burden) and physical outcomes (general physical health, chronic stress [hair cortisol]) and family outcomes (family functioning) over 6 months in parents of technology dependent children, after controlling for the parents' race/ethnicity, sex, family income, and children's functional status. Aim 2: Determine whether changes in psychological and physical outcomes and family outcomes are mediated by changes in parents' levels of resourcefulness (personal and social).

Background

1. Describe the relevant prior experience and gaps in current knowledge describing how it will add to existing knowledge.
2. Describe any relevant preliminary data.

Please add relevant references at the end of the protocol, not at the end of this section.

Introduction/Background

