Caring for a child at home who is dependent on medical technologies such as mechanical ventilation, intravenous nutrition, feeding tubes or tracheostomies, can be a daunting task. Mothers, often the primary caregivers of technology-dependent children, not only manage the demanding care regimens and coordinate the frequent health care and therapy appointments, but must handle many other household responsibilities and perhaps outside employment. Past

research indicates that maintaining the mental health of caregivers and positive family functioning affect the chronically ill child’s growth and development.¹ Toly² found that 39.2% of mothers caring for a technology-dependent child at home (n=103) scored ≥ 16 on the Center for Epidemiological Studies- Depression Scale (CES-D) indicating high risk for clinical depression. Furthermore, 34.9% of the variance in family functioning was explained primarily by level of depressive symptoms, underscoring the impact of such symptoms.² Empirical evidence indicates that resourcefulness training (RT) is an effective cognitive-behavioral intervention that directly contributes to a decrease in negative emotions and depressive cognitions and improved functioning and health³⁻⁵ and it can be implemented on an individual basis in a variety of locales.

This pilot study will provide valuable experience in the development and testing of a RT intervention with mothers of technology-dependent children as well as provide necessary preliminary data regarding effect size for a larger, subsequent intervention study. The study results will also aid in any necessary intervention modifications based upon the feasibility, acceptability, and fidelity information gleaned from participants and interventionists.

Justification/Rationale/Significance of the Study

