In controlled, experimental trials, RT was found to significantly improve resourcefulness,³⁻⁵ adaptive functioning and life satisfaction¹⁵ in elders. RT also improved negative emotions, functioning and depressive cognitions up to 12 weeks post intervention.⁶ While past studies of RT have used a group teaching format/videoconferencing,⁴ two current studies are examining the efficacy of RT using an in-person individual format including grandmothers raising grandchildren.¹⁶ This format is based on research indicating stronger effects for individualized interventions¹⁶. Additionally, this study includes an opportunity to practice and reinforce RT skills taught using expressive writing (EW); personal journaling about specific events. EW has been found to significantly improve physical and psychological health and reduce negative emotions as well as health care visits.¹⁷ While RT has not been tested in young caregivers, equivocal effectiveness is anticipated.

Although children with special health care needs comprise only 16.2% of all children under 18 years, they accounted for 45.5% of the medical expenditures in 2000 due to significantly more out-patient visits, hospitalization, and medications than other children.¹⁸ Children who are technology dependent, while small in number, consume a large proportion of the health care dollars, yet little research has been done to examine how to help promote positive family functioning that will assist in better care for their child.

The study model is based on resourcefulness theory.¹⁹⁻²⁰ Major constructs in the model represent contextual factors, process regulators, resourcefulness (personal, social), and quality of life outcomes. RT is proposed to directly affect all model constructs except contextual factors as indicated by dashed lines. **Contextual factors** include mother’s variables (age, race, income, education), child’s variables (age, level of technology dependence, functional status) and caregiving situation (duration of care, amount of home health care nursing). **Process regulators** (depressive cognitions, depressive cognitions, burden, stress) include variables that mediate effects of contextual factors on resourcefulness. Depressive cognitions are thought patterns that

may lead to depression.²² Assertions that cognitions influence resourcefulness has been validated in women caregivers.¹⁹

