each outcome over time using different residual covariance structures and select the most appropriate structure using likelihood-based criteria. Fixed effects will include a continuous variable to represent time since randomization, an indicator variable to represent the intervention, and stratification factors used during randomization (facility, OTA technology group, sex and race/ethnicity). Assuming a linear rate of change over time, the regression coefficient of the terms representing interactions between time and the intervention indicator variable will be used to estimate the difference in the monthly rate of change in each outcome between the two arms.

To determine if resourcefulness mediates the effect of the resourcefulness intervention on parent outcomes, a model-based causal mediation model^{110,111} will be fit using separate generalized linear models of parent outcomes at 3 months after randomization that adjust for the intervention indicator variable, stratification factors, and the mediator at 6 weeks after randomization. This model will allow us to decompose the total effect of the resourcefulness intervention on maternal outcomes at 3 months into direct and indirect (or mediated) effects and will allow us to estimate the proportion of the total effect that is mediated. Variance estimates, and consequently 95% confidence intervals, will be estimated using a bootstrapping procedure based on 1000 bootstrap samples. To more fully explore the temporal pattern of mediated effects, we will use similar models to also estimate the mediated effect using measurements of the mediator and maternal outcome taken at other time points as well (e.g., total effect of resourcefulness intervention on parent outcomes at 6 months that are mediated by personal or social resourcefulness at 3 months).

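### The mediation models omit measured common causes of resourcefulness and outcome, and the primary model lacks two of the four covariates that Aim 1 names

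*Combined protocol and SAP*

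**What the plan says.** **Aim 1.** The Objectives promise control for race/ethnicity and for "sex, family income, and children's functional status". Table 1 lists the same four variables under Covariates. In the Data Analysis Plan (Primary Analyses), the mixed model contains time, arm and "stratification factors used during randomization (facility, OTA technology group, sex and race/ethnicity". Income and functional status could enter only through the Secondary Analyses, where baseline covariates are screened outcome by outcome at a two-sided level of 0.15.

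**Aim 2.** The Objectives ask whether changes in outcomes are "mediated by changes in parents' levels of resourcefulness (personal and social". The planned models of 3-month outcomes "adjust for the intervention indicator variable, stratification factors, and the mediator at 6 weeks after randomization". They are to "estimate the proportion of the total effect that is mediated", and "95% confidence intervals, will be estimated using a bootstrapping procedure based on 1000 bootstrap samples". No mediator equation is written out. A sensitivity analysis at the end of the section addresses unmeasured confounding.

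**Study model** (Justification/Rationale/Significance). The contextual factors include parent variables ("age, race, income, education") and the child's functional status. They act on resourcefulness through process regulators (depressive cognitions, burden, stress) and also act directly on outcomes. Table 1 schedules resourcefulness and every outcome at enrollment.

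**Facility.** The Primary Analyses call it a randomization factor. The minimization described under Study Design, Procedures and Timeline uses parent gender, technology type and race/ethnicity, and facility is defined nowhere.

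**The concern.** Randomization protects the comparison of arms. It does not protect the path from 6-week resourcefulness to the 3-month outcome. Anything that influences both must be adjusted for, or it is counted as mediation.

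The protocol's own theory identifies such variables. Income and functional status affect both sides. Depressive cognitions, burden and stress are process regulators and also Aim 1 outcomes, and the protocol states that cognitions influence resourcefulness. For those outcomes the enrollment value is therefore a measured common cause under the stated model. For the other outcomes this is a standard inference that the documents do not state.

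Aim 2 is also worded in terms of change, while the models use follow-up levels with no baseline of either variable. At stake are the indirect effect and the proportion mediated, which are the quantities Aim 2 reports.

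**Working it through.** **1. Covariates named and covariates modelled**

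| Variable | Aim 1 and Table 1 | Primary mixed model | Mediation outcome model |
|---|---|---|---|
| Race/ethnicity, sex | yes | yes | yes (stratification factors) |
| Family income, child functional status | yes | no | no |
| Baseline resourcefulness, baseline outcome | not applicable | enrollment outcome is a repeated measure | no |

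**2. Does the Aim 1 omission matter numerically?** Assume an intercept variance of 1, slope variance of 0.01 and residual variance of 0.5, with 123 parents seen at 0, 1.5, 3 and 6 months. The mean visit time is 2.625 and the sum of squared deviations is 19.6875. The variance of one parent's slope is 0.01 + 0.5/19.6875 = 0.0354. The standard error of the difference in slopes is √[0.0354 × (1/61 + 1/62)] = 0.0339 per month. With complete visits, covariates entered as main effects do not touch this within-parent contrast, so it is 0.0339 with or without them. There is no bias and no material loss of precision.

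**3. Set-up for Aim 2.** The documents give no path strengths, so all of those below are assumed. The number analysed is 110 (123 × 0.9 = 110.7). Variances within arm are 1, the arm effect on resourcefulness is a = 0.5 SD, and resourcefulness has no true effect on outcome. The outcome is scored so that higher is better. The indirect effect is a × b, where b is the mediator's coefficient in the outcome model, so its true value is 0. Percentages are from 10,000 simulated trials per setting, with 1,000 bootstrap samples and percentile intervals.

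**4. One omitted covariate**, with paths g to the mediator and d to the outcome. Bias = 0.5 × g × d.

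| g = d | Bias (SD) | 95% interval excludes 0: omitted / included | At 0.05/8, omitted |
|---|---|---|---|
| 0.1 | 0.005 | 3.7% / 3.7% | 0.4% |
| 0.2 | 0.020 | 4.9% / 4.0% | 0.8% |
| 0.3 | 0.045 | 10.9% / 4.2% | 2.0% |

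If the stratification factors already explain a share R² of the covariate, the bias becomes 0.5gd(1 − R²)/(1 − g²R²). At g = d = 0.3 this is 0.0405/0.991 = 0.041 for R² = 0.1, and 0.0315/0.973 = 0.032 for R² = 0.3.

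**5. Both baselines omitted**, with enrollment-to-follow-up correlation ρ for each measure and enrollment correlation r₀ between resourcefulness and outcome. Bias = 0.5 × ρ² × r₀.

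| ρ, r₀ | Bias (SD) | 95% interval excludes 0: omitted / included | 0.05/8: omitted / included | 0.05/16, omitted |
|---|---|---|---|---|
| 0.5, 0.2 | 0.025 | 6.1% / 4.6% | 0.9% / 0.6% | 0.5% |
| 0.6, 0.3 | 0.054 | 14.8% / 5.1% | 3.0% / 0.7% | 1.9% |
| 0.7, 0.4 | 0.098 | 38.4% / 5.5% | 12.8% / 0.9% | 8.8% |

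The plan does not state the Bonferroni divisor. Eight is the number of Aim 1 outcomes; 16 counts two mediators for each.

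**6. Which omission matters most?** Take ρ = 0.6 and r₀ = 0.3, with a covariate correlated 0.2 with mediator and outcome at both times. Writing follow-up as p × baseline + k × covariate, the conditions p + 0.2k = 0.6 and 0.2p + k = 0.2 give p = 0.5833 and k = 0.0833.
- Nothing added: the covariance is 0.3p² + 0.4pk + k² = 0.1285, so the bias is 0.5 × 0.1285 = 0.064.
- Covariate only: 0.5 × (0.1285 − 0.04)/0.96 = 0.046.
- Baselines only: 0.005.
- All added: 0.

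The baselines are the larger part of the remedy.

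**7. On the scale the plan reports.** Reading the anticipated medium effect as a total effect of 0.5 SD (an assumption), a bias of 0.045 to 0.054 SD wrongly labels 0.045/0.5 = 9% to 0.054/0.5 = 11% of the effect as mediated. With b = 0.3 the true indirect effect is 0.15 SD, or 30%. At ρ = 0.6 and r₀ = 0.3, omitting the baselines gave a mean of 0.20 SD (40%) and including them gave 0.15. Power at the 95% level was 74% with the baselines omitted and 81% with them included.

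**The case against.** The strongest reply has five parts.

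- **The Aim 1 and facility mismatches do no harm.** This stands. Alone they are points of wording to reconcile.
- **Aim 2 promises no covariates, is described as exploratory, and already has a confounding sensitivity analysis.** The first two are true, so this is a design weakness and not a broken promise. The sensitivity analysis asks how strong an unobserved confounder would have to be. It starts from an estimate already distorted by observed ones and does not remove that distortion. The 0.15 screen is written for the rate-of-change models.
- **Every size is assumed, and correction makes false mediation rare.** Largely right. Counting 8 Aim 1 tests plus 16 mediation tests, a run of 2,500 trials at 0.05/24 gave 0.4%, 1.4% and 7.1% for the three baseline settings. But the plan also reports estimates with 95% intervals, and their bias does not depend on the significance level.
- **The Background's aim to "provide necessary preliminary data regarding effect size for a larger, subsequent intervention study" most naturally means the randomized intervention effect.** That is a fair reading, so the case should not lean on it. Mediation is a specific aim analysed under Primary Analyses, which is reason enough to estimate it properly.
- **The proposed set may still be incomplete.** By the protocol's logic, baseline cognitions, burden and stress could confound mediation for every outcome, and no mediator equation is written out. Both points stand. The zero bias after adjustment holds only within the assumed model.

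**Conclusion.** The concern holds, and its substance is Aim 2. As written, the mediation models omit measured variables that the protocol's own theory treats as causes of both resourcefulness and outcome, and they omit both baselines.

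The spurious indirect effect is 0.005 to 0.045 SD for one omitted covariate and 0.025 to 0.098 SD for the two baselines. These figures rest on assumed correlations, an assumed 0.5 SD arm effect on resourcefulness and 110 parents. If the true confounding is weak, the harm is small. If enrollment scores track follow-up scores at 0.6 or more and correlate with each other at 0.3 or more, the reported proportion mediated would be misleading by about 10 percentage points or more under the assumed 0.5 SD total effect.

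The Aim 1 omission contradicts the stated aim without biasing the comparison. The plan should be changed before analysis.

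**What to change.** 1. **Aim 2:** write out both the mediator and the outcome equation. In each, adjust for the baseline of the resourcefulness subscale used as mediator, the baseline value of the outcome, family income and enrollment functional status, in addition to the stratification factors.
2. **Other common causes:** state in advance whether parent age, education, child age, duration of care, home nursing and the enrollment process regulators are in or out, for example in one sensitivity model.
3. **Aim 1:** pre-specify family income and functional status as fixed covariates in every primary model. Name the enrollment value of functional status, because Table 1 measures it at all four visits.
4. **Screening:** keep the 0.15 screen only as a labelled sensitivity analysis.
5. **Facility:** remove it from the model if the minimization did not use it. Otherwise define its levels and add it to the randomization description.

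The cost is wording and a few degrees of freedom per model. Every added variable is already collected at enrollment, so no participants, visits or procedures are added. One rule is needed: the pattern-mixture approach is specified for the mixed models only, so parents with no income answer would drop out of the mediation models unless the plan says how they are handled.

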Research Design. A quasi-experimental RCT design with random assignment will be used to test the efficacy of a Resourcefulness Training (RT) intervention compared with an attention control group in mothers and fathers of technology-dependent children. All participants will receive a face-to-face visit from study staff for the T1 data collection. In addition, the intervention group will receive individually tailored RT web based instruction via an approximately 30 minute video that provides details on each of the 8 resourcefulness skills with short examples of application, instruction on journal writing to practice and reinforce use of resourcefulness skills, access to video tapes of parents describing application of resourcefulness skills in the care of their technology-dependent child. Parents will be asked to provide their email address so that we may send them invitation for access to the website that they may visit at any time to access the video tapes. Data will also be collected face-to-face at 3 months (T3) and 6 months (T4) post-intervention. At 6 weeks parents will be emailed a link to the REDCap survey for Time 2 data collection and contacted by phone for SF-12 survey with email reminders. Open-ended questions following their final data collection appointment will allow mothers/fathers to discuss feasibility, acceptability, and fidelity of this intervention and suggestions for potential modification of the intervention and follow up procedures. For this study, 99 female participants and 24 male participants are expected to be enrolled that takes into account 10% attrition.

Measures/Instruments.

The **Depressive Cognition Scale** an 8-item scale ($\alpha = .75$), will measure depressive thought patterns that may lead to depression.⁸ Responses on a 6-point scale range from strongly agree (5) to strongly disagree (0) with a score range 0-40. Items include depressive cognitions such as hopelessness and worthlessness; higher scores indicate more depressive cognitions.

The **Resourcefulness Scale**, a 28-item scale ($\alpha = .85$), will assess both personal (16 items) and social (12 items) resourcefulness.⁹ Responses on a 6-point scale range from extremely descriptive (5) to not descriptive (0) with a score range 0-140; higher scores indicate greater resourcefulness. Construct validity was assessed using confirmatory factor analysis.

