Variable	Measure (Appendix A)	Time of measure				Reliability in previous studies		
Outcome Variables: Parent		Enroll 6 Wk						
		3M	6M					
Psychological and Physical Health	Medical Outcomes Short Form Health Survey (SF-12 version 2)	X	X	X	X	$\alpha=.85-.93$		
Depressive Cognitions	Depressive Cognition Scale	X	X	X	X	$\alpha=.75-.93$		
Depressive Symptoms	Center of Epidemiological Studies- Depression Scale (CES-D)	X	X	X	X	$\alpha=.84-.93$		
Stress	Pediatric Inventory for Parents (PIP)- subjective Hair Cortisol- objective	X	X	X	X	$\alpha=.80-.96$		
		X		X	X	Sensitivity/Specificity=100%		
Burden	Zarit Burden Interview-12	X	X	X	X	$\alpha=.85-.89$		
Outcome Variable: Family		Enroll 6 Wk						
		3M	6M					
Family Functioning	Feetham Family Functioning Survey	X	X	X	X	$\alpha=.73-.83$		
Mediating Variable		Enroll 6 Wk 3M 6M						
Resourcefulness: Personal	Resourcefulness Scale (Personal Resourcefulness Subscale)	X	X	X	X	$\alpha=.83$		
Resourcefulness: Social	Resourcefulness Scale (Social Resourcefulness Subscale)	X	X	X	X	$\alpha=.79$		
Covariates		Enroll 6 Wk 3M 6M						
Parent: · Race/Ethnicity, Gender, Family Income		Enrollment form		X		IRR=1.0		
Technology-Dependent Child: · Functional Status		Functional Status II- Revised		X	X	X	X	$\alpha=.76-.80$
Sample Characteristics		Enroll 6 Wk 3M 6M						
Parent: · Age, Marital Status, Duration of Tech. Dependent Child Caregiver Role		Enrollment form		X			IRR=1.0	
· Education, Amount of Home Nursing Support Services, Lay Caregiving Assistance		Enrollment form		X	X	X	X	IRR=1.0
· Interpersonal Support		Interpersonal Support Evaluation List		X	X	X	X	$\alpha=.88-.90$
Technology-Dependent Child:								

Age	Enrollment form	X				IRR=1.0
Type of Medical Technology Used	Technology Dependency Questionnaire	X	X	X	X	NA

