Sensitivity analyses will also be applied to all mediation models described for the Primary Analysis to evaluate the assumption of sequential ignorability (e.g., no unmeasured confounders of the association between the mediator and each maternal outcome). As described by Imai et al,¹¹¹ this analysis will assess how large an effect an unobserved confounder must have on both models to cause a non-significant mediated effect.

Confidentiality of Specimens and Banking

I am not storing specimens in this research project – *please leave the rest of this section blank*

Describe:

- The source of the specimens* **Hair samples for cortisol level**
- Where the specimens will be stored* **Locked file cabinet in study office**
- How long the specimens will be stored* **Until final data collection then shipped together in one batch to lab for analysis**
- How the specimens will be labeled* **Each hair sample will be labeled with participant ID number and time point sample taken**
- How the specimens will be accessed* **Going into locked file cabinet**
- Who will have access to the specimens* **Members of the research team who have IRB approval.**
- When and how will the specimens be destroyed* **The specimens will be autoclaved and destroyed following processing by the lab.**
- How will the specimens be transported (Please note if transporting specimens, a Material Transfer Agreement (MTA) is required).* **The hair samples are wrapped in foil and enclosed in an envelope. All samples will be shipped next day air FedEx to the lab in a box.**

Describe:

- The procedures to release specimens including:*
 - i. *The process to request a release*

- ii. *Approvals required for a release*
- iii. *Who can obtain specimens*
- iv. *The data to be provided with specimens, including if the data will be identifiable to others* **No data other than ID number and time point.**

For genomic data, please include an attestation of no master list and no attempt will be made to re-identify the specimens.

Are you storing the specimen for future use for other research projects?

- Yes
- No

Confidentiality of Data

1. To maintain the confidentiality of the data:
 - I will use a unique study identifier (not derived from the participants personal identifiers) to code individuals' data and I will store this ID log separate from study data.
 - Other (please explain)

2. How are you storing your electronic data?
 - UH Redcap
 - CWRU Redcap
 - Secure Research Environment (SRE)
 - CWRU Box

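### The Aim 2 mediation models make no allowance for measurement error in the resourcefulness scores; taken alone, this moves about 17-19% (personal) or 21-23% (social) of the indirect effect into the direct effect, with the net bias undetermined

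*Combined protocol and SAP*

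**What the plan says.** Table 1 of the combined protocol and SAP lists the personal and the social subscale of the Resourcefulness Scale as the mediating variables, measured at all four time points. Their alphas, .83 and .79, stand in the column headed "Reliability in previous studies".

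Under Data Analysis Plan, Primary Analyses, the main mediation models take parent outcomes at 3 months and "adjust for the intervention indicator variable, stratification factors, and the mediator at 6 weeks after randomization". Later time points are handled in the same way, for example the "total effect of resourcefulness intervention on parent outcomes at 6 months that are mediated by personal or social resourcefulness at 3 months". The total effect is split into direct and indirect parts, and the text says the model "will allow us to estimate the proportion of the total effect that is mediated". Confidence intervals are "estimated using a bootstrapping procedure based on 1000 bootstrap samples".

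The one sensitivity analysis for these models, at the end of Secondary Analyses, is there to "evaluate the assumption of sequential ignorability", that is, to examine unmeasured confounding between mediator and outcome. The plan describes no latent-variable model, errors-in-variables correction or analysis over a range of reliabilities.

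**The concern.** A scale score with alpha near 0.8 carries random error. Arm is randomized and the mediator is the dependent variable in the arm-to-mediator model, so error there adds noise but no bias. In the outcome model the mediator is a regressor, and error shrinks its coefficient. The total effect does not change, so what leaves the indirect effect reappears as a direct effect of the training. The bootstrap describes sampling variation around the shrunken value and does not restore it.

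The planned sensitivity analysis does not cover this. It asks how strong a confounder must be to make a mediated effect non-significant, which guards against a falsely positive mediation finding. Measurement error works the other way: it can hide mediation.

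Mediation is Aim 2, and the plan hypothesizes that resourcefulness mediates the effect on all study outcomes. The Background says the results will inform a larger trial and changes to the intervention, so the proportion mediated is a figure that later work may use.

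**Working it through.** The documents give no expected mediated effect and no power for mediation, so there is no figure of the plan's own to reproduce.

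**1. Inputs from the documents.** Alpha .83 (personal) and .79 (social), Table 1. Covariates of the outcome model: arm and stratification factors, Primary Analyses. Anticipated effect: medium, with no number (Advanced Plans for Interim or Futility Analysis).

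**2. Assumptions.** A linear model. Classical error that does not differ by arm. Alpha taken as the reliability. No confounding of mediator and outcome, as the plan itself assumes. A 0.5 SD effect of training on the mediator for the worked example.

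**3. Formula.** Let R² be the share of observed mediator variance explained by arm and stratification factors. The mediator-to-outcome coefficient is multiplied by

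λ = (α − R²)/(1 − R²),

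so the share of the indirect effect moved into the direct effect is 1 − λ = (1 − α)/(1 − R²).

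**4. Results.**

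| R² | Personal: 0.17/(1 − R²) | Social: 0.21/(1 − R²) |
|---|---|---|
| 0 | 17.0% | 21.0% |
| 0.059 | 18.1% | 22.3% |
| 0.10 | 18.9% | 23.3% |

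The middle row is arm alone at 0.5 SD: R² = (0.5²/4)/(1 + 0.5²/4) = 0.0625/1.0625 = 0.059. There λ = (0.83 − 0.059)/0.941 = 0.819 and (0.79 − 0.059)/0.941 = 0.777. A true proportion mediated of 50% becomes 0.50 × 0.819 = 41% and 0.50 × 0.777 = 39%.

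**5. Simulation check.** About 110 completers (123 × 0.9 = 110.7), 8,000 replicates, true indirect effect 0.20, true direct effect 0.20, 0.5 SD training effect, no other predictor of the mediator. Mean indirect effect: 0.166 (personal) and 0.155 (social). Mean direct effect: 0.235 and 0.248. The total stays at about 0.40. The shortfalls of 0.034 and 0.045 compare with sampling SDs of the indirect effect of 0.076 and 0.072, ratios of 0.45 and 0.63.

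**6. Effect of an omitted enrollment variable (illustrative values).** Suppose the true coefficient is 0.40 per SD of true mediator score within arm. Suppose one omitted enrollment variable has paths of 0.3 to the mediator and 0.3 to the outcome. Without measurement error the estimate tends to 0.40 + 0.3 × 0.3 = 0.49. With error it tends to 0.49 × 0.819 = 0.401 (personal) or 0.49 × 0.777 = 0.381 (social). Confounding then cancels all or most of the attenuation. Correcting for reliability alone returns 0.49, which is 0.09/0.40 = 22% too high. If the same paths are scaled to the observed score, the corrected values are 0.40 + 0.09/0.819 = 0.51 and 0.40 + 0.09/0.777 = 0.52, or 27% to 29% too high.

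**The case against.** The strongest objection is that the net direction is unknown. The listed outcome model contains neither enrollment resourcefulness nor the enrollment outcome. The protocol's own theory has depressive cognitions influencing resourcefulness, and depressive cognitions are also an outcome. Leaving out such baseline values would be expected to inflate the mediator-to-outcome path. Step 6 shows that modest confounding can offset the attenuation and that a correction for reliability alone can then overshoot. This objection stands, and it shapes the fix.

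It also rules out several stronger readings:

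- A reader might infer that the indirect effect is biased downward by a known amount, so that the plan favours concluding that training works by other routes. The documents do not support this. The alphas come from previous studies, non-differential error is an assumption, and the net sign is open.
- A reader might infer a loss of at least a fifth for both mediators. For the personal subscale it is 17-19% over the range shown, and reaches 20% only at R² = 1 − 0.17/0.20 = 0.15.
- A reader might quote losses of 28% and 35%, from 0.17/0.60 and 0.21/0.60 at an assumed R² of 0.40. That needs covariates such as enrollment resourcefulness, which the listed mediation model does not have. The covariate screen at the 0.15 level in Secondary Analyses is introduced for rates of change, and nothing says it extends to mediation.
- A reader might say the plan declares the scores error-free. It does not. It uses them without correction.

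It can also be said that observed scale scores are an ordinary choice, that the work is described as exploratory, and that no decision rule depends on the proportion mediated. That is fair and limits the weight of the point. It does not remove it: the error is systematic, the planned sensitivity analysis does not address it, and the data for a check are already being collected.

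**Conclusion.** The point holds in limited form. The Aim 2 models take resourcefulness scores with alphas of .83 and .79 at face value, and no planned analysis shows how far this matters. Measurement error alone would move about 17-19% (personal) and 21-23% (social) of the indirect effect into the direct effect when arm and stratification factors explain 0-10% of mediator variance. This rests on a linear model, classical non-differential error, no confounding, and alphas that carry over to these parents. Alpha also omits error that varies from one occasion to the next, which would enlarge the loss.

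The figures describe this one source. The net bias of the reported indirect effect is undetermined, because the omitted enrollment values could push it upward. The total effect and the Aim 1 comparisons are untouched. The weight is modest: this is a cheap improvement to the Aim 2 answer and not a fault that invalidates it.

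**What to change.** Add to the Data Analysis Plan, as a pre-specified sensitivity analysis reported beside the uncorrected result, a reliability-corrected version of each mediation model:

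- Fix the mediator's error variance at (1 − alpha) × its observed variance. Use the trial's own alpha at the mediator's time point (6 weeks for the main models), and repeat over a stated range of reliabilities.
- Bootstrap it in the same way as the planned models.
- Include enrollment resourcefulness and the enrollment value of the outcome as covariates in both the corrected and the uncorrected version, so that the correction does not amplify baseline confounding. This also fits Aim 2, which is framed in terms of changes. These covariates raise R² and so increase the attenuation in the uncorrected version, which is a reason to make both changes together.
- Interpret the corrected result together with the planned analysis of unmeasured confounding, and say that the two biases can act in opposite directions.

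No new data are needed, since the scale is collected at all four time points. The cost is some extra code and wider confidence limits. The corrected estimate still depends on there being no residual confounding, and the enrollment score carries measurement error of its own, so adjustment for it is not complete.
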